### 7.1.2. Descriptive Statistics

Unless otherwise specified, the descriptive statistics shown in the following table will be calculated, depending on the type of the data.

Table 7.1.2. Descriptive Statistics

Data Category	Descriptive Statistics
Categorization/Sequential	Numbers and proportions of subjects
Continuous	Numbers of subjects, mean values, SDs, minimums, maximums, medians

### 7.1.3. Confidence Intervals (e.g., Seroprotection rate, Incidence)

When calculating the confidence intervals for the incidences of adverse events, etc., or the antibody seroprotection rates, the Clopper & Pearson method will be used. Additionally, the 95% confidence interval of the difference between the BK1310 group and the control group in the antibody seroprotection rate will be calculated using the Farrington-Manning method with a lower inferiority margin of 10%.

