## 2.5. Sample Size Justification

○ Target sample size

260 (130 in the BK1310 group and 130 in the control group)

*Rationale*

The objective is to verify noninferiority to the control in each of the anti-PRP antibody seroprotection rate and the antibody seroprotection rates for pertussis, diphtheria toxin, tetanus toxin, and attenuated poliovirus after the administration of 3 doses of BK1310, and the sample size required for this is 119 subjects in each group, 238 subjects in total. To account for dropout rate, the target sample size has been set at 130 subjects in each group, 260 subjects in total. More details are provided below.

The estimated anti-PRP antibody seroprotection rate and antibody seroprotection rates for pertussis, diphtheria toxin, tetanus toxin, and attenuated poliovirus were set as shown below based on the results of study BK1310-J01 (Cohort 2).

Study BK1310-J01 Cohort 2 Results and Estimated Values

	Positive Rate (%)	Estimate
Anti-PRP antibody concentration	100.0	98.0
Anti- pertussis antibody concentration	99.4	99.0
Anti-FHA antibody concentration	97.6	97.0
Anti-diphtheria antibody concentration	97.6	97.0
Anti-tetanus antibody concentration	100.0	99.0
Anti-poliovirus type 1 antibody titer	100.0	99.0
Anti-poliovirus type 2 antibody titer	100.0	99.0
Anti-poliovirus type 3 antibody titer	100.0	99.0

Based on a noninferiority test performed using the Farrington-Manning method, with a lower inferiority margin of 10% and a significance level of 2.5%, one-sided, for the antibody seroprotection rates in the BK1310 and control groups, with a sample size of 119 subjects in each group, the power will be 98.8% for anti-PRP antibodies, 100.0% for PT, 95.7% for FHA, 95.7% for diphtheria, 100.0% for tetanus, 100.0% for poliovirus type 1, 100.0% for poliovirus type 2, and 100.0% for poliovirus type 3. The simultaneous power with a sample size of 119 subjects per group will be 90.3%.

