# 7. STATISTICAL METHODS

## 7.1. General Methods

### 7.1.1. Significance Level and Confidence Coefficient

The test will be one-sided, with a significance level of 2.5%. The confidence intervals will be two-sided confidence intervals, and the confidence coefficient will be 95%.

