#### 7.5.2. Secondary endpoints

##### 7.5.2.1. Anti-PRP Antibody Seroprotection (titer $\geq 0.15$ $\mu\text{g/mL}$ ) Rate After the Primary Immunization

Analysis population(s): FAS

Analysis method: Anti-PRP antibody seroprotection (titer  $\geq 0.15$   $\mu\text{g/mL}$ ) rate after the primary immunization

Analysis method: For each group, for each analysis parameter, the number of subjects, the number of subjects assessed for efficacy, the number of seroprotections, the antibody seroprotection rate (%), and the two-sided 95% confidence intervals will be calculated. Additionally, the 95% confidence intervals of the differences between the BK1310 group and the control group in the antibody seroprotection rates will be calculated.

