### 7.5.3.8. Analyses of Subgroups

#### 7.5.3.8.1. Seroprotection Rates for Each Type of Antibody, by Subgroup

Analysis population(s): FAS

Analysis parameter: The anti-PRP antibody seroprotection (titer  $\geq 1 \mu\text{g/mL}$ ) rate, and also the seroprotection rates for other antibodies (anti-diphtheria, anti-PT, anti-FHA, anti-tetanus, anti-poliovirus serotype 1, anti-poliovirus serotype 2, and anti-poliovirus serotype 3 antibodies) after the primary immunization or the booster immunization.

Analysis method: For the stratification factors shown in Table 7.5.3.8, for each group, the number of subjects, the number of subjects assessed for efficacy for each antibody, the number of seroprotections, the seroprotection rate (%), and the two-sided 95% confidence interval, will be calculated. Additionally, the 95% confidence intervals of the differences between the BK1310 group and the control group in the seroprotection rates will be calculated.

Table 7.5.3.8: Subgroups

Subgroup	
Sex	Male, Female
Age in months	$\geq 2$ and $< 3$ months, $\geq 3$ months
Antibody titer before the first dose in the population in question	For each antibody titer: $<$ reference value, $\geq$ reference value

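### SAP 7.1.3 builds the 10% margin into the 95% confidence interval for a rate difference; at the planned rates that interval covers 99.4 to 99.99% and is 1.2 to 1.5 times as wide as a score interval

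*SAP*

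**What the plan says.** SAP 7.1.3 assigns Clopper-Pearson intervals to single rates. For the between-group difference it says the 95% interval "in the antibody seroprotection rate will be calculated using the Farrington-Manning method with a lower inferiority margin of 10" percent. It gives no formula.

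SAP 7.1.1 sets the standard: "The confidence intervals will be two-sided confidence intervals, and the confidence coefficient will be 95" percent. It sets the test separately: "The test will be one-sided, with a significance level of 2.5" percent.

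SAP 7.5.1 applies the Farrington-Manning test with the 10% limit to the primary rates and asks for 95% intervals of the differences. Intervals for differences are also planned where nothing is tested against −10%:

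- anti-PRP at 0.15 µg/mL after primary immunization, and all rates after the booster (SAP 7.5.2.1 and 7.5.2.2, same wording): "the 95% confidence intervals of the differences between the BK1310 group and the control group in the antibody seroprotection rates will be calculated"
- subgroups (SAP 7.5.3.8.1): "the 95% confidence intervals of the differences between the BK1310 group and the control group in the seroprotection rates will be calculated"

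None of these sections names a method, so 7.1.3 is the only rule for them.

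**The concern.** A margin is an input to a test of one null value. A score interval tries every value of the difference and re-estimates the variance at each, so it has no margin. If the margin enters the interval, the natural meaning is that the variance is held at its value under a difference of −10 points.

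That standard error is right for the one-sided test and for comparing the lower limit with −10. It is wrong for the rest of the interval. At rates of 97 to 99% in both arms, forcing a 10-point gap pushes the fitted BK1310 rate down to about 88 to 90%, where the binomial variance is much larger. The interval is then too wide near a zero difference. The distortion also depends on which arm is ahead, because the null lies on one side only.

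At stake is what the reported intervals say about the size and direction of a difference. Protocol 5.4.1 gives the reason for the non-Hib endpoints as checking whether adding the Hib antigen affects the DPT-IPV response. A modest deficit inside the margin is what a reader would look for there. For the secondary rates, the difference interval is the only planned between-group comparison (titers also get geometric mean ratios).

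**Working it through.** **Inputs.** SAP 2.5: 119 evaluable per group (130 recruited); planned rates 98% (anti-PRP), 97% (FHA, diphtheria) and 99% (the other five), equal in both arms. SAP 7.1.1 and 7.1.3: two-sided 95%, margin 10 points.

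**Step 1: reproduce the plan's power.** Power = Φ((0.10 − 1.96·SE₀)/SE₁). SE₀ uses the restricted maximum-likelihood rates at a difference of −0.10; SE₁ uses the true rates.

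At 97%, the restricted rates are 0.8836 and 0.9836:

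- SE₀ = √[(0.8836·0.1164 + 0.9836·0.0164)/119] = 0.0316
- SE₁ = √(2·0.97·0.03/119) = 0.0221
- Power = Φ(1.72) = 95.7%

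The same formula gives 98.8% at 98% and 99.96% at 99%. The product over eight antigens, 0.9877 × 0.9572² × 0.9996⁵, is 90.3%. All match SAP 2.5. An unpooled variance gives 99.5% at 97%, so the plan's own calculation uses the variance at the −10% null.

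**Step 2: the two intervals.**

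- Fixed-null (plain reading of 7.1.3): d ± 1.96·SE₀, with SE₀ always at −0.10.
- Score: all δ with |d − δ| ≤ 1.96·SE(δ), with the restricted rates re-estimated at each δ.

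**Step 3: coverage and width.** Exact enumeration of both binomials, equal true rates, 119 per group:

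| True rate | Coverage, fixed-null | Coverage, score | Mean width, fixed-null (points) | Mean width, score (points) | Ratio |
|---|---|---|---|---|---|
| 97% | 99.4% | 95.6% | 12.4 | 10.2 | 1.21 |
| 98% | 99.8% | 95.6% | 11.8 | 9.1 | 1.31 |
| 99% | 99.99% | 98.0% | 11.3 | 7.7 | 1.46 |

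At 130 per group the ratios are 1.22, 1.33 and 1.50. With 119/119 in both arms the intervals are ±5.4 and ±3.1 points.

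**Step 4: a noninferior-but-lower result cannot appear.** With p₁ = p₂ − 0.1, the sum p₁(1−p₁) + p₂(1−p₂) is never below 0.09. The half-width is therefore at least 1.96·0.3/√n, which is 5.39 points at 119 and 5.16 at 130. If the lower limit exceeds −10, the upper limit exceeds −10 + 2 × half-width: 0.78 at 119 and 0.31 at 130 (unrounded half-widths). It stays above 0 while n ≤ (2·1.96·0.3/0.1)² = 138 per group.

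**Step 5: example and asymmetry.** Take BK1310 114/119 against control 119/119.

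- d = −5/119 = −4.2 points. The restricted rates are 0.90 and 1.00, so SE₀ = √(0.09/119) = 2.75 points. Fixed-null: −9.6 to 1.2.
- Score: −9.5 to −1.0. Both meet noninferiority; only score excludes 0.
- Arms swapped: fixed-null −2.2 to 10.6, not the mirror image; score 1.0 to 9.5, the exact mirror.

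Chance that the interval excludes 0 in the true direction, 119 per group:

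| True rates, BK1310 vs control | Fixed-null | Score |
|---|---|---|
| 94% vs 99% | 38% | 57% |
| 92% vs 99% | 67% | 79% |
| 99% vs 92% | 46% | 79% |

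**Step 6: the noninferiority decision.** Over all 1,225 tables with 85 to 119 seroprotected of 119 in each arm, the two intervals agreed on whether the lower limit exceeds −10.

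**The case against.** The strongest objection is that 7.1.3 never says the variance is held at −10%. The same pairing of method and margin appears in the power calculation and the test, so the clause may only recall the value against which the lower limit is read. If so, the defect is an unspecified formula. This stands as a limit: the figures are conditional on the plain reading. The sentence still needs changing, because under the other reading the clause has no function and invites the wrong program.

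Other points that stand:

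- In the enumerated grid, the score interval shows BK1310 noninferior yet lower in only two tables: 114 or 115 of 119 against 119 of 119. At equal true rates of 97, 98 and 99% these arise in 0.9, 1.7 and 0.9% of trials, as false signals. At true 94% vs 99% they arise in 6.2%.
- Most trials in which the score interval shows BK1310 worse already fail noninferiority on a primary antigen.
- The excess width shrinks as the arms separate: 1.12 at 94% vs 99% and 1.05 at 92% vs 99%. At assumed subgroup sizes with equal rates it is 1.08 to 1.18 at 60 per arm, and the direction reverses at 30 per arm (0.92 to 0.93).
- The score interval is not exactly nominal: 93.3% at 95% vs 99%, where the fixed-null interval covers 99.1%. At 99% in both arms, part of the over-coverage comes from discreteness.
- No superiority or inferiority conclusion is planned, and rates by arm with their intervals are reported as well.

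The appeal to conservatism does not succeed. Clopper-Pearson is also conservative, but it guarantees its coverage and treats success and failure alike. Here the excess depends on which arm is ahead, and it makes a BK1310 deficit harder to see.

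**Conclusion.** The concern holds. Read plainly, SAP 7.1.3 produces an interval that is labelled 95% but covers 99.4 to 99.99% at the planned rates. It averages 1.2 to 1.5 times the width of a score interval at 119 to 130 per group, and it depends on which arm is ahead. With equal groups of up to 138 it cannot show a noninferior result with a lower BK1310 rate.

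The primary noninferiority conclusion is unaffected. The damage is to the reported differences for primary and secondary rates. It is smaller when the true rates differ, and in small subgroups it fades or reverses.

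This rests on reading the margin clause as fixing the variance, on the SAP 2.5 rates and sample sizes, and on 7.1.3 governing the intervals in 7.5.2.1, 7.5.2.2 and 7.5.3.8.1. It should be corrected before the analysis is programmed.

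**What to change.** Keep the Farrington-Manning test at −10%. Replace the second sentence of SAP 7.1.3 with:

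> Two-sided 95% confidence intervals for all differences in seroprotection rate are obtained by inverting the score test at every value of the difference (Mee type, without the N/(N−1) factor).

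The lower limit then exceeds −10 exactly when the planned test rejects. The version with the N/(N−1) factor can disagree with the test. With 97/119 in both arms, Z is 1.9635 without the factor and 1.9594 with it, on either side of 1.96. That table lies far from the planned rates, so the choice matters for consistency rather than for likely results.

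At a minimum, write out the formula and confine the margin to the test.

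The cost is one SAP sentence and a short program or a different interval option. The test, alpha, sample size and primary conclusion do not change. The sponsor also accepts an interval that can fall slightly below 95% coverage at some unequal rates.

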### 7.1.4. Number of Display Digits

The number of digits displayed will be as follows. Additionally, the digits after the number of display digits will be rounded off (or up), except for the minimum and maximum values.

Table 7.1.4. Number of Display Digits

Descriptive Statistics	Number of Display Digits
Number of subjects	Integers
Proportions	Values rounded off to 1 decimal place
Minimum and maximum values	Same as the number of digits of the original variable
Means, standard deviations, and medians	Number of digits of the original variable + 1

### 7.1.5. Display of Treatment Groups

The display of the treatment groups will be handled as shown in the following table.

Table 7.1.5: Treatment Groups

Treatment Groups	Display
BK1310 group: 0.5 mL per dose	BK1310

Subjects will receive 0.5 mL of each of ActHIB and Tetrabik	Control
---	---------

#### 7.1.6. Tabulation Time Points and Baselines

The tabulation time points will be displayed as shown in the table below.

Table 7.1.6: Tabulation Time Points

Notation for Tabulation		Assessment Time Points in the Protocol
Assessment Time Point	Abbreviation	
Before the first vaccination	V1	Before the first dose at Visit 1
4 weeks after the primary immunization	V4	Postdose examination 1 at Visit 4, and at discontinuation*
Before the booster immunization	V5	Before the fourth dose at Visit 5
4 weeks after the booster immunization	V6	Postdose examination 2 at Visit 6 and at discontinuation**

\* Only at discontinuation after the vaccination of the third dose of the investigational product and before the vaccination of the additional dose

\*\* Only at discontinuation after the vaccination of the additional dose

## 7.2. Subject Disposition

### 7.2.1. Analysis Population Eligibility

Analysis population(s): Randomized subjects

Analysis parameter: Eligibility for the FAS, the PPS, and the safety analysis set (included, not included)

Analysis method: For each analysis parameter, the numbers and proportions of subjects will be calculated by group.

### 7.2.2. Disposition of Discontinued Subjects

Analysis population(s): Randomized subjects

Analysis parameter: Discontinued or completion after the vaccination of the investigational product, reason for discontinuation

Analysis method: For each group, the number and proportion of subjects discontinuing or completing will be calculated. Additionally, for subjects discontinuing, the numbers of subjects for each reason for discontinuation will be output. Additionally, a listing of discontinuations will be prepared.

## 7.3. Demographic and Other Baseline Characteristics

Analysis population(s): FAS, PPS, safety analysis set

Analysis parameter: See Table 7.3

Analysis method: For each parameter, the number and proportion of subjects will be calculated, by group,

for discrete data, and descriptive statistics will be calculated for continuous data. Additionally, if the FAS and the safety analysis set are the same, only the figures for the FAS will be output. In addition, if the FAS is the same as the PPS, then only the FAS will be output. Listings of background information and concomitant medications will also be prepared for all randomized subjects.

Table 7.3: Demographic and Other Baseline Characteristics/Analysis Parameters

Analysis Parameter		Data Category
Sex	Male, Female	Discrete
Age in months		Continuous
	$\geq 2$ and $< 3$ months, $\geq 3$ months	Discrete
Concurrent illnesses	Yes, No	Discrete

#### 7.4. Status of Treatment Compliance

Analysis population(s): Safety analysis set

Analysis parameter: Presence or absence of receipt of a study drug injection

Analysis method: The number of subjects will be calculated for each number of injections (1, 2, 3, 4), by group. Listings will also be prepared.

#### 7.5. Efficacy Analyses

##### 7.5.1. Primary endpoints

Analysis population(s): FAS, PPS

Analysis parameter: The anti-PRP antibody seroprotection (titer  $\geq 1$   $\mu$ g/mL) rate, and the anti-Bordetella pertussis antibody, anti-diphtheria antibody, anti-tetanus antibody, and anti-poliovirus antibody seroprotection rates after the primary immunization

Analysis method: For each analysis parameter, the number of subjects, the number of subjects assessed for efficacy based on each antibody, the number of seroprotections, the antibody seroprotection rate (%), and the two-sided, 95% confidence intervals will be calculated by group. In addition, the differences between the BK1310 group and the control group in the seroprotection rates (%) for each type of antibody, as well as the two-sided, 95% confidence intervals thereof, will be calculated, and noninferiority tests will be applied using the Farrington-Manning method, with a significance level of 2.5%, one-sided, and a lower noninferiority limit of 10%. Moreover, if the antibody seroprotection rate is 100% in both groups, then the test will not be performed, and it will be concluded that noninferiority has been verified.

If the FAS and the PPS are the same, then only the FAS will be output.

##### Rationale for the Lower Noninferiority Limit

In the phase 3 confirmatory studies that have been conducted to assess Hib vaccines and precipitated-purified pertussis/diphtheria/tetanus combined vaccine, 10% has been used as the lower noninferiority

limit for the difference in antibody seroprotection rates. The lower noninferiority limit was therefore set at 10% for this study, as well.

#### 7.5.2. Secondary endpoints

##### 7.5.2.1. Anti-PRP Antibody Seroprotection (titer $\geq 0.15$ $\mu\text{g/mL}$ ) Rate After the Primary Immunization

Analysis population(s): FAS

Analysis method: Anti-PRP antibody seroprotection (titer  $\geq 0.15$   $\mu\text{g/mL}$ ) rate after the primary immunization

Analysis method: For each group, for each analysis parameter, the number of subjects, the number of subjects assessed for efficacy, the number of seroprotections, the antibody seroprotection rate (%), and the two-sided 95% confidence intervals will be calculated. Additionally, the 95% confidence intervals of the differences between the BK1310 group and the control group in the antibody seroprotection rates will be calculated.

##### 7.5.2.2. Antibody Seroprotection Rates After the Booster Immunization

Analysis population(s): FAS

Analysis parameter: The anti-PRP antibody seroprotection (titer  $\geq 1$   $\mu\text{g/mL}$ ) rate, the anti-PRP antibody seroprotection (titer  $\geq 0.15$   $\mu\text{g/mL}$ ) rate after the booster immunization, and the seroprotection rates for other antibodies (anti-diphtheria, anti-PT, anti-FHA, anti-tetanus, anti-poliovirus serotype 1, anti-poliovirus serotype 2, and anti-poliovirus serotype 3 antibodies)

Analysis method: For each group, for each analysis parameter, the number of subjects, the number of subjects assessed for efficacy, the number of seroprotections, the antibody seroprotection rate (%), and the two-sided 95% confidence intervals will be calculated. Additionally, the 95% confidence intervals of the differences between the BK1310 group and the control group in the antibody seroprotection rates will be calculated.

##### 7.5.2.3. Antibody Titer Time Profiles

Analysis population(s): FAS

Analysis parameter: Titers of each type of antibody (anti-PRP, anti-diphtheria, anti-PT, anti-FHA, anti-tetanus, anti-poliovirus serotype 1, anti-poliovirus serotype 2, and anti-poliovirus serotype 3 antibodies)

Analysis method: For each group, for each analysis parameter, the number of subjects, the number of subjects assessed for efficacy, the geometric mean, the geometric standard deviation, the two-sided 95% confidence interval of the geometric mean, and the minimum, median, and maximum values will be calculated. Additionally, the 95% confidence interval of the ratio of the geometric mean in BK1310 group relative to that of the control group will be calculated after the primary immunization or the booster immunization. Listings will also be prepared for all randomized subjects.

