9.2.3 Efficacy Endpoints

9.2.3.1 Antibody Titers

The (sub)investigator or a clinical research coordinator will take blood samples at the following time points in order to measure the subject's antibody titers. The (sub)investigator will record the days of blood sample collection in the case report form.

(1) Sample Collection

- 1) Blood sample collection time points, and volumes collected
 - (a) Times of blood sample collection: Before the first vaccination with the investigational product, at Post-vaccination Examination 1, before the administration of the fourth dose of the investigational product, at Post-vaccination Examination 2, or at discontinuation (only when discontinuation occurs after the vaccination of the third or fourth dose of the investigational product)

Volume of blood collected: Around 3 mL, as a rule

- (b) Number of samples collected: 4

2) Blood processing

The processing of blood will be performed in accordance with the separately prepare "Sample Collection Guidelines."

(2) Shipment of samples

The samples (serum) for antibody titer measurement will be collected by the antibody titer measurement sample transportation organization, and sent to the antibody titer measurement organization.

(3) Measurement Parameters

Hib	Anti-PRP antibody concentration
Diphtheria	Anti-diphtheria antibody concentration
Pertussis	Anti-pertussis antibody concentration
	Anti-FHA antibody concentration
Tetanus	Anti-tetanus antibody concentration
Polio	Attenuated anti-poliovirus antibody titers* (types 1, 2, and 3)

*: Sabin strains

(4) Handling of Remaining Samples

If a new measurement method is established for any of the aforementioned parameters, then the study sponsor will be able to use any remaining samples to measure the antibody titers.

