### 2.3. Randomization Method

In this study, subjects will be randomly assigned to either the BK1301 group or the control group using a variable block method.

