## 4.2. Methods of Tabulation

### (1) Antibody titer geometric mean and geometric standard deviation

Antibody titer geometric mean =  $10^{(\text{mean of the log-transformed value (base 10) of the antibody titer})}$

Antibody titer geometric standard deviation =  $10^{(\text{standard deviation of the log-transformed value (base 10) of the antibody titer})}$

Antibody titer geometric mean 95% confidence interval

=  $10^{(\text{lower limit of the 95% confidence interval of the mean of the log-transformed value (base 10) of the antibody titer})}$  to  $10^{(\text{upper limit of the 95% confidence interval of the mean of the log-transformed value (base 10) of the antibody titer})}$

Antibody titer geometric mean ratio 95% confidence interval

=  $10^{(\text{lower limit of the 95% confidence interval of the difference in the means of the log-transformed values (base 10) of the antibody titers})}$  to  $10^{(\text{upper limit of the 95% confidence interval of the difference in the means of the log-transformed values (base 10) of the antibody titers})}$

However, for the anti-poliovirus antibody titers (anti-poliovirus serotypes 1, 2, and 3 antibody titers), because the data obtained are base 2 log-transformed values, they will be calculated as shown below. In this case, the data obtained will be calculated as “the log-transformed values (base 2) of the antibody titers.”

Antibody titer geometric mean =  $2^{(\text{mean of the log-transformed value (base 2) of the antibody titer})}$

Antibody titer geometric standard deviation =  $2^{(\text{standard deviation of the log-transformed value (base 2) of the antibody titer})}$

Antibody titer geometric mean 95% confidence interval

=  $2^{(\text{lower limit of the 95% confidence interval of the mean of the log-transformed value (base 2) of the antibody titer})}$  to  $2^{(\text{upper limit of the 95% confidence interval of the mean of the log-transformed value (base 2) of the antibody titer})}$

Antibody titer geometric mean ratio 95% confidence interval

=  $2^{(\text{lower limit of the 95% confidence interval of the difference in the means of the log-transformed values (base 2) of the antibody titers})}$  to  $2^{(\text{upper limit of the 95% confidence interval of the difference in the means of the log-transformed values (base 2) of the antibody titers})}$

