## 6.3. Handling of Antibody Titer Data Below the Limit of Quantitation

For the calculation of the descriptive statistics, if the measured antibody titer is below the limit of quantitation, then it will be treated as being the lower limit of quantitation divided by 2.

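### The geometric mean titer ratios are planned without adjustment for the pre-first-dose titer; the comparison is valid but may give up some precision

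*SAP*

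**What the plan says.** SAP 7.5.2.3 plans, at two time points (post-primary and post-booster) and for each of the eight antibodies, that "the 95% confidence interval of the ratio of the geometric mean in BK1310 group relative to that of the control group will be calculated". It names no covariate. SAP 4.2(1) defines the interval by back-transforming the "confidence interval of the difference in the means of the log-transformed values (base 10) of the antibody titers"; polio uses base 2 in the same way. SAP 7.5.3.1, on covariates, says that no adjustment is planned.

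The baseline value is available. Protocol 9.2.3.1 schedules blood samples "Before the first vaccination with the investigational product, at Post-vaccination Examination 1" and at later visits. SAP Table 7.1.6 carries the first of these as time point V1, "Before the first dose at Visit 1".

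Baseline is used elsewhere only to form subgroups. Table 7.5.3.8 lists "Antibody titer before the first dose in the population in question", split at the reference value. SAP 7.5.3.8.1 gives between-group intervals for seroprotection differences within those strata. SAP 7.5.3.8.2 gives geometric means by group within strata but no ratio between groups. A baseline-adjusted titer ratio appears nowhere.

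**The concern.** Leaving out a baseline measurement does not bias a randomised comparison, and the planned interval keeps its coverage. But if a child's titer before dose 1 predicts the titer after vaccination, in either direction, part of the spread in post-dose titers can be explained, and an interval that ignores this is wider than it needs to be.

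The stakes are modest. The geometric mean titers are secondary endpoints with no margin, test or power claim. They do have some weight, because the primary seroprotection rates are assumed to be 97% to 99%, close to the ceiling; the titer ratios give the finer quantitative comparison between the groups.

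**Working it through.** **Inputs.** Evaluable children: 119 per group, N = 238 (Protocol 6.1, SAP 2.5). Two-sided 95% intervals (SAP 7.1.1). The baseline to post-dose correlation of log titers, rho, is not in the documents and is varied as an assumption. So is the post-dose SD on the log10 scale.

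**The plan's own figure.** The plan states no precision for the titer ratios, so there is none to reproduce. The 119 per group comes from the seroprotection power calculation. Asymptotic Farrington-Manning power at the stated rates gives 98.8%, 95.7% and 99.96% for true rates of 98%, 97% and 99%, and a product over the eight antigens of 90.3%, as stated. Adjusting the titer ratios leaves this untouched.

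**Width of the adjusted interval relative to the planned one, log scale:**

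ratio = sqrt[(1 - rho²) × (1 + 1/(N - 4))] × t(0.975; N - 3) / t(0.975; N - 2)

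With N = 238, sqrt(1 + 1/234) = 1.00213 and 1.97011/1.97007 = 1.00002, so the ratio is about 1.0022 × sqrt(1 - rho²).

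The last column is the factor by which the ratio is multiplied and divided to get its 95% limits, assuming SD 0.5 log10. Unadjusted, it is 10^(1.9701 × 0.5 × sqrt(2/119)) = 1.342.

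| rho | width ratio | change | factor, adjusted |
|---|---|---|---|
| 0 | 1.0022 | +0.2% | 1.343 |
| 0.1 | 0.9971 | -0.3% | 1.341 |
| 0.2 | 0.9819 | -1.8% | 1.335 |
| 0.3 | 0.9560 | -4.4% | 1.325 |
| 0.5 | 0.8679 | -13.2% | 1.291 |

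Break-even is at rho of about 0.066. In effective sample size, 119/(1 - rho²) is about 131 per group at rho 0.3 and 159 at rho 0.5. At rho 0.5 the factor goes from 1.193 to 1.165 if the SD is 0.3, and from 1.509 to 1.429 if it is 0.7.

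**Simulation check** (5,000 trials each at rho 0, 0.3 and 0.5; true difference 0; SD 1). The unadjusted estimate averaged 0.001 to 0.002 and its interval covered in 94.9% to 95.5% of trials. Mean half-widths, adjusted against unadjusted, were 0.2554 vs 0.2549, 0.2441 vs 0.2553 and 0.2213 vs 0.2552, in line with the formula.

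**Baselines below quantitation.** Many pre-dose titers may lie below the limit. Setting them to half the limit weakens the correlation. Simulated bivariate normal data with an assumed baseline SD of 0.5 log10 give:

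| share below limit | rho 0.3 becomes | change | rho 0.5 becomes | change |
|---|---|---|---|---|
| 50% | 0.271 | -3.5% | 0.452 | -10.6% |
| 75% | 0.231 | -2.5% | 0.384 | -7.5% |
| 90% | 0.178 | -1.4% | 0.296 | -4.3% |

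**Timing.** By the visit windows, V1 precedes V4 by 3 + 3 + 4 = 10 to 8 + 8 + 6 = 22 weeks. It precedes V6 by 10 weeks plus 6 months to 22 weeks plus 13 months, about 36 to 78 weeks. The correlation, and so the gain, may be weaker for the booster ratios.

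**The case against.** The planned analysis contains no error. The SAP addresses covariates and chooses none, and Protocol 13.3.2.2 asks only that the geometric means be calculated, so the ratio with its interval already goes further. No decision depends on the interval width. The gain rests on a correlation nobody can read from the documents, and on the reported scale it may be small: at rho 0.3 and SD 0.5 the factor moves only from 1.342 to 1.325, or to about 1.332 with 75% of baselines below the limit. An adjusted ratio also will generally not equal the quotient of the two group means printed beside it, and reporting both gives 32 ratios instead of 16.

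Most of this stands as a limit on importance. The size of the gain is unknown and the point is optional. It does not remove the asymmetry: the worst cost is about 0.2% of interval width, while a moderate correlation buys several percent without further enrolment or blood sampling. The mismatch with the displayed means is met by keeping the unadjusted ratio in the report. The stratified seroprotection comparisons in SAP 7.5.3.8.1 do not serve the same purpose, because they concern rates, not titer ratios.

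Two qualifications are correct. Lack of bias also requires that missing post-dose titers be unrelated to outcome, since the FAS leaves out children with no post-primary result; baseline adjustment does not by itself cure that. And the half-limit rule in SAP 6.3 is confined to descriptive statistics, so the outcome in the model needs it as much as the covariate. Both apply equally to the planned unadjusted ratio.

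**Conclusion.** The concern holds, as a minor and optional improvement. The planned ratios are valid but take no account of a baseline value already collected. At 119 per group the possible narrowing on the log scale is negligible for rho up to 0.1, about 4% at 0.3 and about 13% at 0.5, and less where many baselines are below quantitation. These figures assume a linear relation between log titers and an assumed rho, which may differ by antigen and time point. The primary noninferiority tests, the sample size and the 90.3% power are unaffected.

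**What to change.** Before database lock, amend SAP 7.5.2.3 and 7.5.3.1 so that each post-primary and post-booster ratio comes from ANCOVA on log titer (base 10; base 2 for polio), with group and the V1 log titer of the same antibody.

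- Use V1 at both time points, not V5: V5 follows three doses, and adjusting for it could remove part of the vaccine effect.
- Widen SAP 6.3, which now begins "For the calculation of the descriptive statistics, if the measured antibody titer is below the limit of quantitation", so that half the limit is also used for the covariate and the outcome in this model.
- Retain children without a V1 value by a rule set in advance, such as a missing-baseline indicator.
- Report the unadjusted ratio as supporting. Age category is an optional further covariate.
- Leave the primary analysis as planned.

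Protocol 13.4 allows a change before lock with its reason recorded in the SAP and study report; after lock, an adjusted ratio would have to be shown apart from the planned results. The cost is SAP text and a few lines of code on existing data, about 0.2% in width if rho is 0 (marginally more with extra terms), and 8 × 2 = 16 supporting ratios beside the 16 adjusted ones.
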